### 5.3.5.2. Analysis Methods

The analysis of progression-free survival on first-line therapy for MM will be similar to the analysis of primary endpoint PFS described above. Two supplementary analyses will be performed, 1) subjects who die due to COVID-19 will be censored at the last disease assessment prior to the death; and 2) subject who missed at least 2 consecutively scheduled visit prior to the PFS2 event will be censored. Visit schedule is every 6 months after initial PD. Subject will be censored at the date of last visit prior to the PFS2 event if the PFS2 event date and the latest date

of scheduled visit immediately preceding the event differs more than 2.5 times the disease evaluation intervals (i.e. 15 months), which indicates that subject missed at least 2 consecutively scheduled visit. .

### **5.3.5.3. Best Response on first-line Therapy for MM**

Subject's best response while on first-line therapy is determined based on investigator assessment per the IMWG response criteria. The number and percentage of subjects in the following response categories will be tabulated by treatment group: sCR, CR, VGPR, PR, stable disease (SD), progressive disease (PD), and not evaluable (NE). The overall response (including sCR, CR, VGPR, or PR), VGPR or better (sCR, CR, or VGPR), and CR or better (sCR, or CR) will also be summarized. For each of the above categories, two-sided 95% Clopper-Pearson exact confidence interval (CI) will also be presented by treatment group.

## **5.3.6. Overall Survival**

### **5.3.6.1. Definition**

Overall survival is measured from the date of randomization to the date of death due to any cause. Subjects who are lost to follow-up will be censored at the last known alive date. Subjects who died after consent withdrawal will be considered as having an OS event. Subjects who are still alive at the clinical cut-off date for the analysis or the survival status is unknown will be censored at the last known alive date. The date of last known alive will be determined by the maximum collection/assessment date from among selected data domains within the clinical database.

### **5.3.6.2. Analysis Methods**

The analysis of overall survival will be similar to the analysis of primary endpoint PFS described above. As a supplementary analysis, OS will be analyzed with subjects who die due to COVID-19 censored, i.e. deaths due to COVID-19 will not be counted as OS events.

## **5.3.7. Incidence of MM with adverse prognostic factors**

### **5.3.7.1. Definition**

Incidence of MM with adverse prognostic factors is defined as progression to International Staging System (ISS) III MM (based on  $\beta$ 2-microglobulin), MM with adverse cytogenetic characteristics (FISH findings of del(17p), t(4;14), t(14;16) or amp(1q21)), or r-ISS III MM (based on  $\beta$ 2-microglobulin, LDH and adverse cytogenetic characteristics).

### **5.3.7.2. Analysis Methods**

Proportions of subjects who progress to MM with adverse prognostic factors will be tabulated and two-sided 95% Clopper-Pearson exact confidence intervals (CI) will be presented by treatment group.

### **5.3.8. Duration of Response**

#### **5.3.8.1. Definition**

Duration of response(DOR) is calculated from the date of initial documentation of a response (PR or better) to the date of first documented evidence of progression to MM based on the computerized algorithm, according to IMWG criteria or death due to any cause, whichever occurs first.

Subjects who start subsequent anti-cancer therapies without PD will be censored at the date of the last disease assessment prior to the start of subsequent anti-cancer therapies. Subjects who have not progressed or subjects who die due to causes other than disease progression will be censored at the last disease assessment date.

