2.1.2. Endpoints

Primary Endpoint

The primary endpoint of this study is PFS (defined as the time from the date of randomization to the date of initial documented progression to MM according to the IMWG diagnostic criteria for MM or the date of death, whichever occurs first).

Secondary Endpoints

To demonstrate additional clinical benefit, the following secondary endpoints will be evaluated:

- Time to biochemical or diagnostic (SLiM-CRAB) progression defined as the earlier of time to the earlier of biochemical progression or diagnostic (SLiM-CRAB) progression (see Section 9.2.2)
- Overall response rate (ORR), defined as, the proportion of subjects with a PR or better as defined by the IMWG response criteria
- Complete response (CR) rate, defined as, the proportion of subjects with a CR (or better) as defined by the IMWG response criteria
- Time to first-line treatment for MM, defined as, the time from the date of randomization to the date of the first-line treatment for MM
- Progression-free survival on first-line treatment for MM (PFS2), defined as, the time from the date of randomization to the date of documented progressive disease (PD) on the first-line treatment for MM or death, whichever comes first
- Overall survival (OS), defined as, the time from the date of randomization to the date of death
- Incidence of MM with adverse prognostic features, which include International Staging System Stage III (based on β 2-microglobulin and albumin) and adverse cytogenetic characteristics

- Serum daratumumab PK concentrations and parameters including minimum observed concentration (C_{min}) and maximum observed concentration (C_{max})
- Incidence of anti-daratumumab antibodies and anti-rHuPH20 antibodies
- Change from baseline in global health status and emotional functioning scales of the European Organization for Research and Treatment of Cancer (EORTC) quality of life questionnaire (QLQ)-C30, future perspective scale of the EORTC QLQ-MY20, and utility and visual analog scale of the European Quality of Life Five Dimensions Questionnaire (EQ-5D-5L)
- Duration of response, defined as date of onset of first response until date of disease progression or death
- Time to response, defined as the time from randomization until onset of first response

Exploratory Endpoints

- Identification of novel biomarkers in relation to PFS/OS

Refer to Section 9, Study Evaluations for evaluations related to endpoints.

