- Duration of response: A descriptive summary for duration of response will be provided. No statistical comparison will be made.
- Time to response: A descriptive summary for time to response will be provided. No statistical comparison will be made.

In the event that the primary endpoint is statistically significant, details of the hierarchical testing of the secondary endpoints will be provided in the Statistical Analysis Plan.

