## AMENDMENT HISTORY

SAP version	Issue date
Original SAP	18 April 2018
Amendment 1	November 2, 2020
Amendment 2	December 16, 2020

Summary of the major changes in SAP Amendment 2:

- a) Removed interim superiority analysis per the feedback from FDA. Only interim futility analysis will be performed,
- b) Revised the definition of duration of response to include death due to any cause.
- c) Added a censoring rule for subjects with missing visits for PFS2 as an additional supplemental analysis

Summary of the major changes in SAP Amendment 1::

- a) More details were provided for the spending function for ORR, PFS2 and OS in Section 5.1.1.
- b) Description of the primary estimand was added in Section 5.2.
- c) Supplemental analyses for the primary endpoint and key secondary endpoints were added in Sections 5.2.3 and 5.3.
- d) ISS staging subgroups and risk category subgroups based on Mayo 2018 risk criteria were added in Section 2.4.
- e) An imputation rule was added for partial subsequent anticancer therapy start date.
- f) Added additional exploratory analysis to support HEMAR (Attachment 1).

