**Table 4: PFS Event and Censoring Method**

Situation	Date of Progression or Censoring	Outcome
No postbaseline disease assessment	Randomization	Censored
Disease progression prior to start of anti-cancer therapy for multiple myeloma	Earliest date that indicates disease progression	PFS event
Death prior to start of anti-cancer therapy for multiple myeloma	Date of death	PFS event
Other, such as: 
 
○ Withdrawal of consent to study participation,
 
○ Lost to follow-up
 
○ Start of subsequent anti-cancer therapy prior to disease progression or death
 
	Date of last disease assessment on or prior to withdrawal of consent to study participation, lost to follow-up, or start of subsequent anti-cancer therapy	Censored

Note, Subjects who were already diagnosed multiple myeloma per baseline central imaging review will be censored at randomization.

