#### **5.3.8.2. Analysis Methods**

Analysis of DOR will be based on subjects who achieved a response of PR or better. Median DOR with 95% CI will be estimated based on the Kaplan-Meier method for each treatment group. The Kaplan-Meier curve for DOR will be plotted by treatment group.

No formal statistical comparison of DOR between the treatment groups will be made.

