**2. ENDPOINTS FOR SUBGROUP ANALYZES**

As described in Sections 5.2 (Primary Efficacy Endpoints), 5.3 (Secondary Endpoints) and 9.1 (Patient-Reported Outcomes), the following endpoints will be evaluated by subgroups as defined in Section 1, Appendix:

- PFS
- Time to Biochemical or SLiM-CRAB progression
- ORR
- Time to first-line treatment for MM
- PFS2
- OS
- Duration of response
- Time to Response
- EORTC QLQ-C30, EORTC QLQ-MY20, EQ-5D-5L (Section 9.1.1.1)
- PRO: Time to worsening/improvement (Section 9.1.1.2)
- Time to progression
- Incidence of MM with adverse prognostic features

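### SAP 5.3.8.1 makes every death a duration-of-response event and then censors deaths not due to progression; the censoring clause is the wrong one

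*SAP*

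**What the plan says.** The DOR definition in SAP 5.3.8.1 has three parts.

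- The first paragraph runs DOR from the first response of PR or better to progression by the computerised algorithm, "according to IMWG criteria or death due to any cause, whichever occurs first".
- The second paragraph begins with responders who start another anti-cancer therapy before progression. They are censored at the last assessment before that therapy.
- Its last sentence censors responders who have not progressed and adds that "subjects who die due to causes other than disease progression will be censored at the last disease assessment date".

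Protocol 2.1.2 lists the endpoint as "Duration of response, defined as date of onset of first response until date of disease progression or death", with no limit on the cause of death. The SAP Amendment History gives as one purpose of Amendment 2: "Revised the definition of duration of response to include death due to any cause".

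On use, SAP 5.3.8.2 plans a Kaplan-Meier median with 95% CI and a curve for each group, and adds: "No formal statistical comparison of DOR between the treatment groups will be made". Protocol 11.3.2 agrees: "A descriptive summary for duration of response will be provided. No statistical comparison will be made". SAP Attachment 1 states that "the following endpoints will be evaluated by subgroups as defined in Section 1, Appendix", and its list includes DOR.

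**The concern.** Take a responder who dies of a cause other than myeloma, with no progression and no subsequent therapy. Under the first paragraph this is an event on the date of death. Under the last sentence it is a censored observation at the previous assessment. A programmer has to choose, and the choice changes the output.

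The two choices also estimate different things. Counting the death gives time in response until progression or death, which is the protocol endpoint. Censoring it treats the dead responder as someone who could still have progressed later. That lengthens the estimated median and lifts the curve. At stake are the DOR summaries for each arm and any DOR subgroup results produced under Attachment 1.

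**Working it through.** **Step 1. Can the two sentences be reconciled?**

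| Responder's course | First paragraph | Second paragraph |
|---|---|---|
| Progresses | Event | Not addressed |
| Starts another therapy before progression | Not addressed | Censored at last assessment before therapy |
| Alive, no progression | Not addressed | Censored at last assessment |
| Dies of another cause, no progression, no other therapy | Event at death | Censored at last assessment |

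Only the last row conflicts. The subsequent-therapy rule does not remove the conflict, because it is a separate sentence about different subjects.

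**Step 2. Which sentence is wrong?**

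- Protocol 2.1.2 ends DOR at progression or death without regard to cause.
- SAP Amendment 2 set out to bring all deaths into the definition. This is used only as evidence of intent; both conflicting sentences stand in the current SAP.
- PFS (SAP Table 4) counts death before myeloma therapy as an event dated at death. BOD-PFS (SAP 5.3.1.1) also counts deaths of any cause before such therapy.
- Where the SAP wants a cause-specific rule, it states one coherently. For time to first-line treatment (SAP 5.3.4.1), death from progression is an event and other deaths are censored. The stray DOR clause would suit a definition of that kind, so it is probably a remnant of the pre-Amendment 2 definition. That last step is an inference.

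**Step 3. How much would the censoring clause matter?**

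The documents give no planning figure for DOR, so there is none to reproduce. The inputs are therefore assumptions:

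- f, the share of DOR events that are deaths without progression: not in the documents; taken as 2%, 5% and 10%.
- M, the median DOR with all deaths counted: not in the documents. For scale only, M = 48 months, the planning median PFS for daratumumab in Protocol 11.2. That figure runs from randomization, not from response.
- Constant (exponential) hazards.

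The total hazard is h = ln 2 / M, and the hazard of progression alone is (1−f)h.

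- All deaths counted: S(t) = 0.5^(t/M), median M.
- Other deaths censored: S(t) = 0.5^((1−f)t/M), median M/(1−f).

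The inflation factor 1/(1−f) does not depend on M. At t = 24 months and M = 48, the correct rate is 0.5^0.5 = 70.7%, and the censored version is 0.5^(0.5(1−f)).

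| f | 1/(1−f) | Median, correct → censored (months) | 24-month rate, correct → censored |
|---|---|---|---|
| 2% | 1.020 | 48.0 → 49.0 | 70.7% → 71.2% |
| 5% | 1.053 | 48.0 → 50.5 | 70.7% → 71.9% |
| 10% | 1.111 | 48.0 → 53.3 | 70.7% → 73.2% |

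The closed form ignores that the clause dates censoring at the last 12-weekly assessment rather than at death. Under the planned 24 months of accrual and 24 months of further follow-up (Protocol 11.2), follow-up from randomization runs from 24 to 48 months, and is shorter from response. A median as long as 48 months might not be reached by then, and the effect would show in the curve instead.

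**The case against.** The strongest reply is that the slip has little practical reach. The first paragraph, the protocol definition and the declared aim of Amendment 2 all agree, so a programmer had a clear basis for the right rule. DOR carries no test. Active monitoring involves no disease-specific treatment, so responders are presumably mostly in the daratumumab arm and there is little between-arm contrast to distort. The Attachment 1 subgroups are exploratory and conditional on the data. The share f may also be low: subjects enter with ECOG 0 or 1, and Protocol Table 5 shows no Grade 5 event among 41 + 41 + 40 = 122 subjects in the earlier smoldering myeloma study. All of this stands as a limit on weight, although the Table 5 evidence is early and covers treatment-emergent events only.

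It might also be argued that the last sentence is a specific exception to a general rule. That does not stand. An exception for every death not due to progression would leave the all-cause wording with no meaning.

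A reader might infer three stronger points that the documents do not support:

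- That the reported DOR is in fact overstated. Nothing shows which rule was programmed.
- That the inflation is as large as a quarter. That needs f = 20%, since 1/(1−0.2) = 1.25, and the documents offer no basis for such a share.
- That a treatment comparison or a trial conclusion is biased. No DOR comparison is planned.

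**Conclusion.** The point holds. SAP 5.3.8.1 is wrong as written: two current sentences assign different outcomes to the same death, and no other part of the documents reconciles them. The censoring clause is the one to remove.

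The consequence is conditional on that clause having been programmed. In that case the DOR median is too long by about 2%, 5% or 11% for assumed shares of 2%, 5% or 10%, given exponential hazards. The direction is certain if any such deaths occurred; the size is not known from the documents. DOR is outside the tested sequence of ORR, PFS2 and OS (SAP 5.1.1), so type I error, power, sample size and the primary result are untouched. This is a modest correction to a descriptive secondary endpoint.

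**What to change.** Keep the sentence on subsequent anti-cancer therapies. Replace the whole of the last sentence with two rules:

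- *A death from any cause that precedes subsequent anti-cancer therapy is a DOR event.*
- *Responders who remain alive and free of progression at clinical cut-off are censored at their last disease assessment.*

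Deleting only the clause about other causes of death is not enough. The remainder would still censor everyone who has not progressed, and read literally that includes a responder who dies without progressing. The cut-off rule should follow the text of SAP 5.2.1, because SAP Table 4 has no cut-off row.

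No error is alleged for withdrawal or loss to follow-up. If the sponsor wants that explicit for DOR, the Table 4 date can be used: "Date of last disease assessment on or prior to withdrawal of consent to study participation, lost to follow-up, or start of subsequent anti-cancer therapy".

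Then confirm which rule the derivation program applied. If it applied the censoring clause, re-run the DOR median, confidence interval and curve, and any Attachment 1 DOR subgroups already produced.

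The cost is a short SAP correction, a program check and possibly a re-run on existing data. No new data are needed, and under Protocol Amendment 6 response assessments are no longer collected. The primary analysis has concluded and the study is unblinded, so the change should be documented as implementing the definition already in Protocol 2.1.2. The downside for the sponsor is a possibly shorter reported DOR.

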#### **5.3.8.2. Analysis Methods**

Analysis of DOR will be based on subjects who achieved a response of PR or better. Median DOR with 95% CI will be estimated based on the Kaplan-Meier method for each treatment group. The Kaplan-Meier curve for DOR will be plotted by treatment group.

No formal statistical comparison of DOR between the treatment groups will be made.

### **5.3.9. Time to Response**

#### **5.3.9.1. Definition**

Time to response (i.e., time to first response) is defined as the time from the date of randomization to the date of initial documentation of a response of PR or better based on the computerized algorithm, according to IMWG response criteria.

#### **5.3.9.2. Analysis Methods**

For subjects who achieve a response of PR or better, descriptive statistics (n, mean, standard deviation, median, and range) will be provided to summarize TTR for the responders in each treatment group.

## **6. SAFETY**

Analysis of safety data will be provided on the safety analysis set. All subjects will be analyzed according to the actual treatment they received.

The safety assessments to be evaluated include AEs, deaths, clinical laboratory tests (hematology, chemistry), electrocardiogram (ECG) and ECOG performance scores.

### **6.1. Adverse Events**

AEs will be recorded in standard medical terminology and graded according to the National Cancer Institute Common Terminology Criteria for Adverse Events (NCI-CTCAE), Version 4.03. For AE reporting, the verbatim term used in the CRF by investigators to identify adverse events will be

coded using the latest version of Medical Dictionary for Regulatory Activities (MedDRA) coding dictionary.

The relationships to study medication will be recorded as not related, doubtful, possible, probable, or very likely on eCRF for all the AEs. Adverse events will be categorized and summarized according to their highest relationship to study medication. An adverse event is considered as related to study medication if the relationship is recorded as possible, probable or very likely.

For subjects treated with daratumumab, treatment-emergent adverse events (TEAEs) are defined as any AE with onset date and time on or after that of the first dose through 30 days after the last study drug administration, or the day prior to start of subsequent therapy, whichever is earlier; or the follow-up AE (linked to an existing TEAE) with onset date and time beyond 30 days after the last study agent administration but prior to the start of subsequent therapy; or any AE that is considered related to (very likely, probably, or possibly related) study medication regardless of the start date of the event. AEs with missing or partial onset date and time will be considered as treatment-emergent unless the onset date and time of an AE can be determined as earlier than that of the first dose, or later than 30 days after last study drug administration. For subjects on active monitoring, treatment-emergent adverse events will be defined as AEs that occur after randomization and prior to start of subsequent therapy, or prior to discontinuation from the study or if the subject continues on study for 3 years, then up to 30 days after that, whichever is earlier.

Unless otherwise specified, at each level (e.g., system organ class and/or preferred term) of subject summarization in reporting the incidence of the AE, a subject is counted once if one or more events were recorded. For summarizing new onset events, all event records of the same preferred term from the same subject are to be linked by the onset date and the end date. If an event is followed by another event of the same preferred term with an onset date (or date/time) the same as or 1 day (or 1 minute if applicable) after the end date (or date/time) of the previous record and any features of the adverse event (i.e.: toxicity grades/seriousness/action taken) are different between these two records, these 2 records should be linked together and considered as 1 event. A Grade 5 event will be linked to previous event of the same preferred term if the onset date of Grade 5 record is the same or one day after the end date of previous record.

### **6.1.1. Overview of TEAEs**

An overview of TEAEs reported through the study will be provided for each treatment group. Overall summary of TEAE will include the subjects with TEAEs, serious TEAEs, TEAEs related to study treatment, TEAEs of maximum toxicity grade of 1 to 5, TEAEs leading to treatment discontinuation, TEAEs leading to dose modification (delay within cycle, cycle delay, or dose skipped), and TEAEs with fatal outcome.

A similar overview of TEAEs will be presented by treatment cycle.

### **6.1.2. All TEAEs**

The following summaries will be provided for all TEAEs:

- TEAEs by system organ class (SOC) and preferred term (PT)
- Most common ( $\geq 10\%$ ) TEAEs by SOC and PT
- Most common ( $\geq 10\%$ ) TEAEs by PT

### **6.1.3. Toxicity Grade 3 or 4 TEAEs**

The following grade 3 or 4 TEAEs will be summarized:

- Grade 3 or 4 TEAEs by SOC and PT
- Most commonly reported ( $\geq 5\%$ ) grade 3 or 4 TEAE by SOC and PT

A similar summary of grade 3 or 4 TEAEs will be presented by SOC, PT and by study week.

In addition, a listing of grade 3 or 4 TEAEs will also be provided.

